2.7.3 Laboratory data

All laboratory samples will be processed through the central laboratory. Laboratory data consist of hematology, biochemistry and urinalysis measurements, including plasma cortisol. All data will be listed with abnormal values flagged.

Laboratory data measured more than 7 days after last inhalation of study drug are regarded as post-treatment data and will not be summarized, only listed. All data will be included in the analyses regardless of rescue medication use.

The following analyses will be performed by treatment:

- absolute values and change from baseline summarized for continuous laboratory parameters by visit and time point
- frequency table of results for categorical laboratory parameters by visit and time point
- shift tables relative to the normal reference ranges summarizing the change from baseline to most extreme post-baseline value for each continuous laboratory parameter
- shift tables from baseline to the worst post-baseline value for categorical laboratory parameters
- the number and percentage of patients with newly occurring or worsening laboratory abnormalities meeting the clinically notable criteria (see [Appendix 16.1.9](#) for definition of notable values) summarized by laboratory parameter, scheduled post-baseline visit and time point and additionally at any time on treatment considering all post-baseline data from scheduled, unscheduled and premature discontinuation visits

The by-visit/time point summaries will include the worst case post-baseline values (determined from all post-baseline data even if from unscheduled and premature discontinuation visits, if not measured more than 7 days after last dose). To determine the worst case, the direction of interest (maximum and/or minimum value) is tabulated for hematology and biochemistry

parameters in [Appendix 16.1.9](#). For continuous urinalysis parameters the direction of interest is always "High" (maximum value).

For a patient to meet the criterion of a newly occurring clinically notable value, the patient needs to have a baseline value that is not clinically notable for that parameter. For a patient to meet the criterion of a worsening clinically notable value, the patient needs to have a baseline value that is clinically notable and also have a worse post-baseline value. For patients with missing baseline value, any post-baseline notable value will be considered as newly occurring. A listing of all patients with notable laboratory values will be provided.

The maximum change from baseline will be summarized for liver parameters (ALT, AST, alkaline phosphatase, total bilirubin).

Furthermore, the number and percentage of patients with newly occurring or worsening abnormalities in liver function tests (LFT) will be summarized by treatment and scheduled post-baseline visit and time point and additionally at any time on treatment considering all post-baseline data from scheduled, unscheduled and premature discontinuation visit (if not measured more than 7 days after last dose) based on the following criteria:

Notable liver function test values

Criterion
ALT > 3 x the upper limit of normal range (ULN) ALT > 5 x ULN ALT > 8 x ULN ALT > 10 x ULN ALT > 20 x ULN
ALT or AST > 3 x ULN ALT or AST > 5 x ULN ALT or AST > 8 x ULN ALT or AST > 10 x ULN ALT or AST > 20 x ULN
Total bilirubin > 1 x ULN Total bilirubin > 1.5 x ULN Total bilirubin > 2 x ULN Total bilirubin > 3 x ULN
ALP > 1.5 x ULN ALP > 2 x ULN ALP > 3 x ULN ALP > 5 x ULN
ALT or AST > 3 x ULN and total bilirubin > 1.5 x ULN ALT or AST > 3 x ULN and total bilirubin > 2 x ULN ALT or AST > 5 x ULN and total bilirubin > 2 x ULN ALT or AST > 8 x ULN and total bilirubin > 2 x ULN ALT or AST > 10 x ULN and total bilirubin > 2 x ULN ALT or AST > 20 x ULN and total bilirubin > 2 x ULN
ALP > 3 x ULN and total bilirubin > 2 x ULN ALP > 5 x ULN and total bilirubin > 2 x ULN
ALT or AST > 3 x ULN and Total Bilirubin > 2 x ULN and ALP < 2 x ULN (Hy's law)
ALT or AST > 3 x ULN and (nausea or vomiting or fatigue or general malaise or abdominal pain or (rash and eosinophilia))*

ALT = alanine aminotransferase, AST = aspartate aminotransferase, ALP = alkaline phosphatase

* Based on the signs/symptoms information as recorded on the liver events eCRF, not the adverse events eCRF.

When a criterion contains multiple laboratory parameters, the criterion will only be considered to have been met when all conditions occur at the same time (i.e., within the same sample). A case where all criteria are met at a post-baseline time point will be considered as newly occurring if the criteria are not met at baseline and will be considered as worsening if the criteria are met at baseline and at least one component is worsening from baseline irrespective of whether the other(s) are better.

Listings of patients with clinically notable LFT values will be provided.

During the trial, there has been an unexpected high reporting rate of elevated potassium by Central Lab, which was investigated and in the end considered clinically irrelevant and no risk

to patient safety. Central Lab was notified to flag all the elevated potassium data. As additional analyses, potassium data without flagged values will be summarized.

2.7.4 Vital signs

Vital signs measurements include systolic and diastolic blood pressure (SBP and DBP), pulse rate (measured at Visit 101, 102, 201, 202, 204, 207, 210, 214, EOT – early treatment discontinuation), and body weight (measured at Visit 101, 207, 214, EOT – early treatment discontinuation).

Vital signs data measured more than 7 days after last inhalation of study drug are regarded as post-treatment data and will not be summarized, only listed. All data will be included in the analyses regardless of rescue medication use.

The following analyses will be performed by treatment:

- absolute values and change from baseline summarized by parameter, visit and time point
- the number and percentage of patients by parameter, visit and time point with
 - pulse rate < 40 bpm, 40 – 90 bpm, and > 90 bpm
 - SBP < 90 mm Hg, 90 – 140 mm Hg, and > 140 mm Hg
 - DBP < 50 mm Hg, 50 – 90 mm Hg, and > 90 mm Hg
- the number and percentage of patients with newly occurring or worsening notable vital signs values (see [Appendix 16.1.9](#) for definition of notable values) summarized by parameter, scheduled post-baseline visit and time point and additionally at any time on treatment considering all post-baseline data from scheduled, unscheduled and premature discontinuation visits

The by-visit/time point summaries will include the maximum and minimum post-baseline SBP, DBP, and pulse rate values (even if from post-baseline unscheduled and premature discontinuation visits, if not measured more than 7 days after last dose).

The same approach as for notable laboratory values will be used to define a newly occurring notable vital sign value and a worsening notable vital sign value.

A listing of all patients with notable vital sign values and changes will be provided.

2.7.5 Electrocardiogram (ECG)

ECG measurements include ventricular rate, QT interval, RR interval, PR interval, QRS duration, and Fridericia's QTc (calculated as $QTcF = QT / \sqrt[3]{RR}$ (in seconds), where $\sqrt[3]{}$ denotes the cube root). Furthermore, an overall interpretation of the central cardiologist will be provided as well as a specification of abnormal findings.

ECG data measured more than 7 days after last inhalation of study drug are regarded as post-treatment data and will not be summarized, only listed. All data will be included in the analyses regardless of rescue medication use.

The following analyses will be performed by treatment:

- absolute values and change from baseline summarized by parameter, visit and time point
- the number and percentage of patients with newly occurring or worsening notable QTcF values (see [Appendix 16.1.9](#) for definition of notable values) summarized by scheduled

[figure not shown]
post-baseline visit and time point and additionally at any time on treatment considering all post-baseline data from scheduled, unscheduled and premature discontinuation visits

- frequency table of results for overall ECG interpretation (normal, abnormal) by visit and time point
- the number and percentage of patients with ECG abnormalities summarized by evaluation type, abnormality finding, visit and time point. In addition, the number and percentage of patients with newly occurring or persistent/recurrent ECG abnormalities at any time point over the treatment period (considering all post-baseline data from scheduled, unscheduled and premature discontinuation visits) will be summarized by evaluation type and abnormality finding

The by-visit/time point summaries will include the maximum QTcF and maximum ventricular rate (even if from post-baseline unscheduled and premature discontinuation visits, if not measured more than 7 days after last dose).

The same approach as for notable laboratory values will be used to define a newly occurring notable QTc value and a worsening notable QTc value.

A listing of all patients with notable QTc values and changes will be provided.

2.9 Interim analysis

2.9.1 Data Safety Monitoring Board (DMC)

An independent, external data safety monitoring board (DMC), comprising experts (as defined in the Charter) will be set up to review all serious adverse events (including deaths and all hospitalizations) and pneumonia. DMC members will review this data generated externally and independently of Novartis, at predetermined intervals. If significant safety issues arise in between scheduled meetings, ad-hoc meetings will be scheduled to review the data. Based on the safety implications of the data, the DMC may recommend modification or termination of the study.

It is planned that the independent DMC will review semi-blinded (i.e., treatment group named as A, B, C, D, or E) safety data. The details of the information flow, confidentiality and specific analyses required for the safety monitoring analysis will be documented in the DMC Charter. The Charter will be finalized prior to semi-blinding the data for the safety monitoring analysis. Since the purpose of the DMC is not based on efficacy for stopping rule, there will be no alpha spent for the safety monitoring analysis. [REDACTED]

2.9.2 Primary analysis after all patients have completed at least 26 weeks treatment

The primary and key secondary endpoints of CQVM149B2301 study are the trough FEV₁ and ACQ-7 after 26 weeks of treatment, respectively while the entire study treatment period is 52 weeks. In order to support a marketing authorization filing once all patients have completed 26 weeks of treatment (V207) or prematurely withdrawn from the study, an interim database freeze will be conducted to perform the Primary Analysis.

The database for Primary Analysis will contain data up to 26 weeks for all patients and data up to 52 weeks for patients who have completed the study. For patients who are ongoing at the time of interim database freeze, the database will include data available until last completed visit.

Primary analysis includes primary and key secondary endpoints as well as other pre-specified endpoints at Week 26. [REDACTED]

At the time of interim database freeze for Primary Analysis, a limited number of pre-specified Sponsor members will be unblinded to the study data to work on study and submission related activities which require knowledge of these data.

The study will continue under the management of a separate blinded team who will be responsible for study conduct from the time of the 26 week interim database freeze until end of study. In order to maintain the integrity of the study data, the blinded team members will not have access to any of the unblinded data or results. In addition, all patients and investigators will remain blinded.

Two separate CSRs will be published:

- Primary Analysis CSR: To support analyses once all patients have completed the assessments after 26 weeks of treatment (Visit 207) or prematurely withdrawn from the study. This will include analysis of primary and key secondary as well other pre-specified endpoints which are evaluable at this time.
- Full CSR: To support analysis once all patients have completed the assessments after 52 weeks of treatment (Visit 214) plus follow up (Visit 301) or prematurely withdrawn from the study.

Since the analysis of primary and key secondary objectives will be performed only for the Primary Analysis CSR, the interim analysis will not require any adjustment to the overall type I error rate.

2.10 Sample size calculation

The sample size calculation takes into account the following consideration:

1. To achieve at least 90% power (with multiplicity adjustment) for primary endpoint trough FEV₁ with a treatment difference of 100 mL between QMF149 vs. MF at the corresponding doses, assuming standard deviation of 380 mL based on internal studies QMF149A2210, QMF149E2201, QMF149E2203 and literature data;
2. To achieve at least 80% power (with multiplicity adjustment) for key secondary endpoint ACQ-7 with a treatment difference of 0.15 between QMF149 vs. MF based on pooled doses, assuming standard deviation of 0.80 based on studies QMF149A2210, QMF149E2201, QMF149E2203 and Kerstjens (2012).

If 10% dropout rate is assumed, then calculation shows the sample size of 2000 patients (i.e., 400 per arm) will provide 94% power for item 1 and 85% power for item 2, with multiplicity adjustment.

The sample size calculation was performed in R 3.2.3.

3 Analyses to be reported outside of CSR

3.1 Subgroup analyses

Subgroup analyses for Japanese, Chinese, and Asian patients will be performed for the FAS to explore the treatment effect in respective sub populations.

Asian subgroup contains patients from the following countries:

- China
- Japan
- Rep of Korea

The following endpoints will be summarized and/or analyzed for all three sub populations using similar methods as described in previous sections, if not marked with special symbol.

- Patient disposition
- Protocol deviations

[figure not shown]
- Analysis sets
- Demographics
- Disease characteristics
- Spirometry at run-in visits and at baseline
- Trough FEV₁
- ACQ-7
- Pre-dose trough FEV₁*
- Trough FVC*
- Pre-dose trough FVC*
- Mean morning/evening PEF*
- Asthma symptom based on e-diary*
- Rescue medication*
- Asthma exacerbations*
- Asthma Quality of Life Questionnaire (AQLQ-S+12)*

[figure not shown]

[figure not shown]
- Exposure
- Concomitant asthma medications
- Laboratory data
- Vital signs
- ECG
- Adverse events

*: only needed for Japanese subgroup analyses

The specific outputs for each sub population under each endpoint will be specified in the TFLs.

Clinical Study Report - Appendix 16.1.9 Documentation of statistical methods

16.1.9.1 Introduction

This appendix gives details about statistical methods in addition to the report text. All analyses will be performed by using SAS Version 9.4.

16.1.9.2 Major protocol deviations and other exclusion criteria

The following protocol deviations will be considered as major and will lead to exclusion of patients from analysis sets:

Exclusions from per-protocol set:

- INCL01: Age < 12 years or > 75 years or missing
- INCL03: No current diagnosis of persistent Asthma of at least 12 months prior to V1
- INCL04.A4: Patient not treated with medium/high dose ICS or LOW dose ICS/LABA combination for at least 3 months and/or not at stable dose 30 days prior to Visit 1
- INCL05: ACQ score < 1.5 at V101 and/or V102
- INCL05.01: ACQ INVALID ASSESSMENT; Patient used invalidated ACQ7 at Visit 101 and/or Visit 102.
- INCL06.A4: Pre- Bronchodilator FEV1 at V101 and V102 < 50% or \geq 85% of predicted normal at visit 101
- INCL06.01: Patient has not achieved assessments according to ATS/ERS criteria
- INCL07: Patient has not achieved an acceptable spirometry result and does not have historical reversibility or bronchoprovocation
- INCL07.01: Patient has not achieved an acceptable spirometry result and does not have Historical reversibility or bronchoprovocation according to ATS/ERS as per source documentation
- EXCL01: Patient has a smoking history of > 10 pack years or missing
- EXCL01.01: Patient smoked or inhaled tobacco within the 6 month period prior to V1
- EXCL01.02: Patients smoking nicotine inhaler at inclusion.
- EXCL02: Asthma attack/exacerbation requiring SCS or hospitalization or ER visits within 6 weeks prior to V1
- EXCL03: History of severe asthma exacerbation requiring intubation prior to visit 1
- EXCL05: Asthma exacerbation within 4 weeks prior to V1
- EXCL05.01: Respiratory Tract Infection or asthma worsening between screening and run-in 102 visits
- EXCL05.02: Respiratory Tract Infection within 4 weeks prior to V1
- EXCL06: Visual clinical significant oropharyngeal candidiasis between visit 1 and visit 102
- EXCL07: Chronic condition affecting upper respiratory tract
- EXCL08: Patient has a history of chronic lung diseases other than asthma

- EXCL11: Investigational drugs used within 5 half lives or until the return of baseline pharmacodynamic effect whichever is longer
- EXCL24: Patient is not on maintenance immunotherapy for allergies for at least 3 months prior to V101
- EXCL27: Unable to use dry powder inhaler device at V101 and/or V201
- EXCL28: Patient has history of alcohol or other substance abuse
- EXCL33.A4: Use of LAMA within 3 months prior to Visit 101
- OTH08: Patient not having correct run in medication (i.e. 100mcg accuhaler or 125 mcg via MDI inhaler) or dose equivalent
- COMD07: Use of parenteral or oral corticosteroids less than 4 weeks prior to visit 101
- COMD08: Intra muscular corticosteroid less than 3 months prior to Visit 101
- COMD09: Use of Ige inhibitor less than 4 months prior to visit 101
- COMD10: Xanthine's use less than 7 days prior to visit 101
- COMD12: Last LABA washout more than 4 days prior to visit 101 or last ICS wash out more than 7 days before visit 101
- OTH06: Compliance failure of the patient influencing the safety and efficacy data as per investigator judgement
- OTH04: Patient receiving investigational drug other than study drug during the course of the study
- COMD05: Leukotriene antagonists and leukotriene synthesis inhibitors taken less than 7 days prior to visit 101
- COMD06: Use of SABA other than rescue medication, not discontinued at Visit 1
- COMD11: LABA taken less than 48h before Visit 101
- COMD01: Banned asthma related Concomitant medication
- WITH01: More than 5 exacerbation and still on treatment
- WITH02: Adolescent patient experience one severe exacerbation requiring hospitalization (ER>24) and is still on treatment

Exclusions from full analysis set and per-protocol set:

- OTH05: Patient Randomized more than one Trial.
- OTH14: Patient randomized more than once into this trial

Exclusions from full analysis set, per-protocol set, safety set, [REDACTED]:

- OTH02: Patient randomized but did not receive study drug

Exclusions from randomized set, full analysis set, per-protocol set, [REDACTED]:

- Patient received study drug but was not randomized

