4.1 Inclusion criteria

Patients eligible for inclusion in this study must fulfill all of the following criteria:

1. Male and female adult and adolescent patients aged ≥ 12 years old (or ≥ 18 years old depending upon regulatory and/or IRB/IEC/REB approval and/or country participation) and ≤ 75 years

2. Written informed consent must be obtained before any study-related assessment is performed. Patients below the legal age of consent are required to have the Informed Consent Form signed by the patient's parent / guardian; adolescents are required to sign an assent form
3. Patients with a documented diagnosis of asthma for a period of at least 1 year prior to Visit 1 (Screening)
4. Patients who have used medium or high dose ICS (please refer to [Appendix 11](#) for guidance) or low dose of LABA/ICS combination for asthma for at least 3 months and at stable doses for at least 1 month prior to Visit 1
5. Patients must be symptomatic at screening despite treatment with mid or high stable doses of ICS and/or combinations of ICS (low dose) with long-acting beta adrenergic agent. Patients must have ACQ-7 score ≥ 1.5 at Visit 101 and at Visit 102 (prior to double-blind treatment) and qualify for treatment with medium or high dose LABA/ICS
 - In case that the spirometry is repeated due to a failure of meeting criteria 6, ACQ-7 should be repeated as well.
6. Pre-bronchodilator $FEV_1 \geq 50\%$ and $< 85\%$ of the predicted normal value for the patient according to ATS/ERS criteria after withholding bronchodilators (see [Table 5-2](#)) at both Visit 101 and 102
 - Withholding period of bronchodilators prior to spirometry:
 - SABA for ≥ 6 hours
 - FDC or free combinations of ICS*/LABA for ≥ 48 hours
 - SAMA for ≥ 8 hours
 - xanthines ≥ 7 days

Washout period of each drug should be kept as close as possible as above and should not be longer. If wash-out period is considered to be longer, please contact your Novartis Medical Monitor

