19. Patients who have not achieved an acceptable spirometry results at Visit 101 in accordance with American Thoracic Society/European Respiratory Society (ATS /ERS) criteria for acceptability and repeatability. Repeat spirometry may be allowed in an ad-hoc visit scheduled as close as possible from the first attempt (but not on the same day) if the spirometry did not qualify due to ATS/ERS criteria at Visit 101 and/or Visit 102. If the patients fail the repeat assessment, the patients may be rescreened once, provided the patients return to their treatment prior until rescreened
20. Patients receiving any medications in the classes listed in [Table 5-3](#)
21. Patients receiving any asthma-related medications in the classes specified in [Table 5-2](#) unless they undergo the required washout period prior to Visit 101 and Visit 201 and follow the adjustment to treatment program.
22. Patients receiving medications in the classes listed in [Table 5-4](#) should be excluded unless the medication has been stabilized for the specified period and the stated conditions have been met.

23. Patients with severe narcolepsy and/or insomnia.
24. Patients on Maintenance Immunotherapy (desensitization) for allergies or less than 3 months prior to Visit 101 or patients on Maintenance Immunotherapy for more than 3 months prior to Visit 101 but expected to change throughout the course of the study.
25. Patients who are serving a custodial sentence, do not have a permanent residence or who are detained under local mental health legislation/regulations.
26. Patients who are directly associated with any members of the study team or their family members.
27. Patients unable to use the Concept1 dry powder inhaler, Twisthaler[®], Accuhaler[®] or a metered dose inhaler. Spacer devices are not permitted for rescue medication.
28. History of alcohol or other substance abuse.
29. Patients with a known history of non-compliance to medication or who were unable or unwilling to complete a patient diary or who are unable or unwilling to use Electronic Peak Flow with e-diary device.
30. Patients who do not maintain regular day/night, waking/sleeping cycles (e.g., night shift workers).
31. Pregnant or nursing (lactating) women, where pregnancy is defined as the state of a female after conception and until the termination of gestation, confirmed by a positive hCG laboratory test.

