Tricyclic antidepressants (Please note that tetracyclics which are similar in class with regards to drug interaction are also to be excluded)	14 days

Class of medication¹	Minimum cessation period prior to Run-in (Visit 101)
Other investigational drugs	30 days or 5 half-lives, whichever is longer
Noradrenaline reuptake inhibitors	7 days
Live attenuated vaccine	30 days

¹ This table is not considered all-inclusive. Medications should be assessed for adherence to the indication and other inclusion/exclusion criteria. The wash-out of these prohibited medications is not to be encouraged. Treatment for AEs including asthma events are permitted if required. However if it is transitioning to chronic treatment, the investigator should contact Novartis Medical Monitor.

Table 5-4 Medications allowed under certain conditions

Class of medication	Condition
Mucolytic agents not containing bronchodilators	If stabilized for at least 4 weeks prior to Visit 1 and throughout the trial.
Pure Selective Serotonin Reuptake Inhibitors (they must have no documented effect on any other neurotransmitters or other biological pathways. e.g. muscarinic pathway)	Treatment regimen is stable for at least one month at Visit 1.
Inactivated influenza vaccination, pneumococcal vaccination or any other inactivated vaccine	Not administered within 48 hours prior to a study visit.
Intra-nasal corticosteroids	Stable dose for at least 4 weeks prior to Visit 101 In the case of prn, provided an established pattern of use has been documented.
Antihistamines (e.g. loratadine, cetirizine)	If stabilized for at least 4 weeks prior to Visit 1 and throughout the trial. In the case of prn, provided an established pattern of use has been documented.
Topical corticosteroids for the treatment of eczema	In recommended doses and dosage regimens
Maintenance immunotherapy for allergies	Stable dose for at least 3 months prior to Visit 101 and unchanged throughout study treatment.

If indicated for the treatment of an adverse event including asthma exacerbation, any treatment deemed necessary for the safety of the patient is allowed from the start of the event (defined as per protocol [Section 6.4.5](#) for asthma exacerbation) until the event is resolved. If it is required as chronic treatment, the investigator should contact/discuss with Novartis Medical Monitor. Patients may NOT self-medicate (other than administration of rescue medication) or adjust therapy without permission/guidance from treating physician.

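### Two per-protocol exclusion codes in SAP 16.1.9.2 (EXCL24 and INCL06.A4) do not match the protocol criteria they implement

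*SAP*

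**What the plan says.** **Immunotherapy.** Protocol 4.2, criterion 24, has two limbs. The first excludes "Patients on Maintenance Immunotherapy (desensitization) for allergies or less than 3 months prior to Visit 101" (the word before 'less' is a slip; the protocol summary has 'for'). The second excludes patients on "Maintenance Immunotherapy for more than 3 months prior to Visit 101 but expected to change throughout the course of the study". Table 5-4 in Protocol 5.4.8 lists maintenance immunotherapy among conditionally allowed medications, the condition being "Stable dose for at least 3 months prior to Visit 101 and unchanged throughout study treatment". Nothing in either place requires a patient to be on it. The matching SAP code is "EXCL24: Patient is not on maintenance immunotherapy for allergies for at least 3 months prior to V101".

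**FEV1 range.** Protocol 4.1, criterion 6, requires pre-bronchodilator FEV1 of at least 50% and below 85% of predicted "at both Visit 101 and 102". The SAP code opens "INCL06.A4: Pre- Bronchodilator FEV1 at V101 and V102 < 50% or" and, after a greater-than-or-equal sign, closes "85% of predicted normal at visit 101".

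**Status of the list.** Protocol 9.1 leaves major deviations to be defined in the SAP before database lock and unblinding. SAP 2.2 points to Appendix 16.1.9 for the list, and 16.1.9.2 states that the listed items lead to exclusion from analysis sets. The PPS serves one purpose: repeating the primary MMRM in protocol adherers (SAP 2.2 and 2.6.1.4).

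**The concern.** The list in 16.1.9.2 is the operative definition of the PPS. If a code does not say what its criterion says, the set is either programmed as written, with the wrong patients in or out, or repaired by judgement during programming. SAP 2.9.2 has some sponsor staff unblinded at the Week 26 freeze. A repair made after that point is no longer a rule fixed before unblinding. At stake is whether the one analysis meant to describe protocol adherers uses a set whose membership was correctly pre-specified.

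**Working it through.** The documents state no figure on this point, so the check sets each code against its criterion, patient type by patient type.

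**EXCL24 against criterion 24**

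| Patient | Deviation under criterion 24? | Flagged, literal reading | Flagged, if code is applied to users only |
|---|---|---|---|
| Never on immunotherapy | No | Yes (wrong) | No |
| On it under 3 months | Yes | Yes | Yes |
| On it over 3 months, stable | No | No | No |
| On it over 3 months, change expected | Yes | No (wrong) | No (wrong) |

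The literal reading misclassifies two of four types. The users-only reading misclassifies one. The second limb of criterion 24 is lost either way. The list's general code for banned asthma-related medication (COMD01) is not an evident substitute, since immunotherapy sits in Table 5-4 as conditionally allowed.

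**INCL06.A4 against criterion 6**

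Four readings of the code are possible:
- A: out of range at Visit 101.
- B: below 50% at both visits, or at least 85% at Visit 101.
- C: out of range at both visits.
- D: out of range at either visit.

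| FEV1 pattern | Deviation under criterion 6? | A | B | C | D |
|---|---|---|---|---|---|
| In range at both | No | No | No | No | No |
| Low at 101 only | Yes | Yes | No | No | Yes |
| High at 101 only | Yes | Yes | Yes | No | Yes |
| Low at 102 only | Yes | No | No | No | Yes |
| High at 102 only | Yes | No | No | No | Yes |
| Low at both | Yes | Yes | Yes | Yes | Yes |
| High at both | Yes | Yes | Yes | Yes | Yes |

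Only D matches criterion 6 throughout, and D has to ignore the closing reference to Visit 101. The neighbouring code INCL05 (ACQ score) uses and/or for the same two visits, so the intended form was at hand. INCL06.01 concerns ATS/ERS quality, not the percent-predicted range, and does not fill the gap. Failure at Visit 102 only is a realistic pattern: patients switch to low-dose fluticasone at Visit 101 (Protocol 3.1) and spirometry is repeated at Visit 102 (Table 6-1).

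**What the literal EXCL24 would do (illustration only)**

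The documents give no prevalence of immunotherapy, so p, the share of 2000 patients on it for at least 3 months, is assumed. The PPS is then capped at 2000p, or n = 400p per arm. Power for 100 mL with SD 380 mL (SAP 2.10), two-sided 5%, normal approximation, is Φ(100 / (380√(2/n)) − 1.96). As calibration, n = 400 × 0.9 = 360 gives 94.2%, beside the 94% stated in SAP 2.10.

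| Assumed p | PPS at most | Per arm | Power |
|---|---|---|---|
| 1% | 20 | 4 | 6% |
| 5% | 100 | 20 | 13% |
| 10% | 200 | 40 | 22% |
| 20% | 400 | 80 | 38% |

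**The case against.** The strongest reply is that EXCL24 is a label, not a program. Section 16.1.9.2 introduces its items as protocol deviations, and SAP 2.2 defines the PPS by the absence of major ones. A patient who never had immunotherapy has breached nothing, so the code is most naturally shorthand for users whose therapy was too recent. SAP 2.2 also mentions a validation analysis plan, which may hold more detail. The list is a selection (exclusions 4, 9, 10 and 12 to 18, for example, have no code), so dropping the second limb could be deliberate. If non-users were removed by mistake, the tabulation of exclusions in SAP 2.3.1 would show it at once.

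Much of this stands, and it limits what may be inferred:
- A reader might call EXCL24 inverted. It is not: it flags short-term users and keeps stable long-term users, as intended. It is over-broad on its literal wording, and incomplete.
- A reader might conclude that the PPS will be nearly empty. That needs the literal reading, which the introduction to the list makes unlikely in practice.
- A reader might say that INCL06.A4 plainly ignores Visit 102. The code names Visit 102 and then contradicts itself.

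The reply does not remove the mismatch. The users-only reading still omits a limb of criterion 24, and no reason for that is given. INCL06.A4 matches criterion 6 only if some of its words are disregarded.

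**Conclusion.** Both codes are wrong as written and should be corrected. EXCL24 flags all non-users if taken literally and omits the expected-change limb on any reading. INCL06.A4 misses a patient out of range only at Visit 102 on every reading that keeps its closing words, and readings B and C also miss some patients out of range only at Visit 101.

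The consequence is modest. Only the supportive PPS analysis of trough FEV1 is affected. A reader might take this as a threat to the primary result, but the primary analysis uses the FAS, and the all-measurements MMRM and tipping-point analysis in SAP 2.6.1.4 do not use the PPS either. The number of misclassified patients cannot be derived from the documents. The caps of 20 to 400 patients rest on an assumed prevalence of 1% to 20% together with the literal reading, and are not a forecast.

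**What to change.** Amend two lines of SAP 16.1.9.2 before the Week 26 database freeze:

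- EXCL24: *Patient on maintenance immunotherapy for under 3 months before V101, or for more than 3 months with a change expected during the study.*
- INCL06.A4: *Pre-bronchodilator FEV1 below 50%, or at or above 85%, of predicted at V101 and/or V102.*

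With these wordings all four immunotherapy types and all seven FEV1 patterns above agree with the protocol. The EXCL24 text should keep to an expected change, as criterion 24 does. An actual change during treatment is the separate condition in Table 5-4 and would need its own code if the sponsor regards it as major. If the second limb was left out on purpose, the SAP should say so.

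The cost is two lines, in a section that SAP Amendment 2 has already corrected once. The one-word slip in protocol criterion 24 can be put right at the same time. No data collection, sample size or primary analysis changes.
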